**\*Please enter the study short title:**

Fc glycan composition in human immunity

\* This field allows you to enter an abbreviated version of the Study Title to quickly identify this study.

**Is this Study using Subject Management?**

Yes  No

### 4.0 Rockefeller University Conflict of Interest

**4.1 Investigator Financial Conflict of Interest** All KSP must complete an annual certification of their Significant Financial Interest ("SFI") disclosures in the University's online Research Administration System at <https://RAS.rockefeller.edu>. Disclosures also must be updated in connection with new human subjects research protocols ("Research Certification"), and within 30 days of discovering or acquiring a new SFI. To avoid delays in the IRB review process, when prompted by an email from [[contact]](mailto:[contact]) requesting an updated Research Certification, KSP should click on the Research Certification link contained in that email notification, or go to <https://RAS.rockefeller.edu>, to (a) review and update his or her SFI disclosures or certify that he/she has no updates, as appropriate, and (b) indicate whether any of his/her SFI disclosures are reasonably related to the design, conduct, or reporting of the research protocol. If a KSP discloses a SFI that might constitute a conflict of interest with respect to the proposed protocol, he or she must e-mail a copy of the Lay Summary of the draft protocol to [name], Esq. ([[contact]](mailto:[contact])). Doing so will facilitate addressing COI issues in step with the development of the study protocol. Non-compliance or tardiness in making or updating COI disclosures will result in a delay in IRB review. [Institutional Conflict of Interest](#):

As early as possible the PI (or a designee) preparing a clinical research protocol must review a list of entities in which The Rockefeller University has an Institutional Financial Interest at <https://icoi.rockefeller.edu/account/login.php>. If the proposed study involves any entity on that list, the PI (or designee) must notify [name], staff to the FCOI Committee, by e-mail [[contact]](mailto:[contact]) and [name], Chair of the IRB, by email: [[contact]](mailto:[contact]), provide the name(s) of the entities and a copy of the Lay Summary. Doing so will facilitate addressing institutional COI issues in step with the development of the study protocol. Failure to take steps to review and address potential institutional conflicts of interest will delay the IRB review process.

### 6.0 Delegation of Authority

**6.1 Enter authorized activities for all [Rockefeller University personnel](#) named on the study.**

**Activity Codes:**

1. Informed consent **	11. Participant recruitment	21. Skin biopsy *
2. Inclusion / exclusion criteria	12. Perform assays	22. Conduct sleep study
3. Medical/medication history *	13. Specimen / sample analysis	23. Diet design and preparation
4. Perform Physical Exam *	14. Lumbar puncture *	24. Nutritional assessment and counseling
4a. Write / Sign LIP orders *	15. Femoral line placement *	25. Addition of PABA to food
5. Skin assessments and photos	16. Central line placement *	26. Data analysis
6. Study drug dispensing *	17. Insulin clamp procedure *	27. Data review
7. Study drug administration *	18. Leukapheresis *	28. Data management
8. Study drug reconciliation	19. Sigmoidoscopy *	29. Maintain regulatory documents / files
9. Study drug compliance	20. Fat biopsy *	30. Complete CRF's
10. Administer study questionnaire(s)		

**Add up to three additional authorized activities specific to this study (do NOT add activities that have previously designated codes):**

31:	
32:	
33:	

**Activity Codes Continued:**

- 34. Behavioral Testing
- 35. Bod Pod
- 36. Bone Marrow Aspiration \*
- 37. Neuropsychological Testing \*
- 38. Conduct Focus Group
- 39. Conduct Smell Study
- 40. Genetic Counseling \*
- 41. Apply EEG Electrodes \*\*
- 42. Olfactometer Test
- 43. Study Participant Teaching
- 44. Resting Energy Expenditure
- 45. Source Document Review & Correction
- 46. Medical Photography
- 47. See 4a
- 48. Adverse Event Assessment
- 49. Clinical Trial Registration
- 50. Study Support Drug Dispensary
- 51. Internal Monitoring
- 52. Randomization

**Enter the authorized activities for External Personnel:**

Name	Title	Authorized Activities	Start Date	End Date
No results found				

## 7.0 Study Description

7.1

### Study Classification

Full Review

7.2

### \* Submission Request Category

**Note:** For each submission, please designate the level of review, or "Submission Request Category" you are requesting. When completing this field, please indicate the level of review you are requesting for the specific submission you are working on.

For example, if you are submitting an Expedited Amendment request to change the Key Study Personnel on your existing Full Board study, you should select "Expedited Review" in both the Amendment Submission Form and Study Application. The IRB will confirm an Expedited review of the Amendment submission is appropriate, and the overall study will remain classified as a full Board review. Please see the help bubble for guidance.

**To submit a request for a Not Human Subjects research determination, please exit this form and select the "Not Human Subjects Research Determination" form under Create a New Study.**

- Exempt from Review
- Exempt with Limited Review
- Expedited Review
- Full Review

### 7.3 \* Lay Summary

**Please provide a summary of your study in lay language that is easily understood by a non-scientist. The summary should be no more than half a page (500 words or less) and should contain a clear statement of the rational for the study.**

Please provide a summary of your study in lay language. The summary should be no more than a half page (500 words or less) and should contain a clear statement of the rationale for the study.

Antibodies are principle mediators of immunity against infections and they can also give rise to autoimmune and inflammatory diseases. Two functional domains make up an IgG antibody – the Fab domain binds to a specific target, while the Fc domain can interact with receptor molecules to activate a pro- or anti- inflammatory state. The Fc domain of IgGs contains a glycan that is variable in composition and its specific sugar components are an important determinant of the biologic activity of IgGs in both protective and pathologic immune responses. New disease treatments could be developed through purposeful manipulation of IgG Fc glycans, but there is currently little known about how Fc glycan composition is regulated. We plan to study this by evaluating whether vaccination or infection can cause changes in Fc glycan composition and, if so, whether signaling from helper T cells, age of the patient, and/or route of vaccine administration are determinants of specific modifications that are triggered by vaccination. Next, we will study effects that specific components within the Fc glycan have on immunity against the common human pathogens *Streptococcus pneumoniae* and influenza viruses using *in vitro* and *in vivo* models of infection.

## 7.4

### \* Public Health Impact Statement

Provide a brief plain language statement (100 words or less) of the value of the research proposed and its potential impact on population health. Additional instructions located in Help.

In order to produce better more effective vaccines, it is important to understand the particulars of why individuals have an effective or ineffective immune response to vaccination. We are going to examine specific aspects of the antibody (IgG Fc glycan) made by healthy volunteers who receive different vaccines or who have a viral infection to understand the nature of an effective (or less effective) vaccine response. The results of this research could be used to develop adjuvants to increase/ improve vaccine response.

## 8.0

### Clinical Trial Registration

#### 8.1

#### Clinical Trial Registration

The types of studies listed below must be registered at **Clinical Trials website** before enrolling the first participant in order to be in compliance with federal regulations and preserve the opportunity to publish the study in journals that adhere to the **ICMJE guidelines**. Please check the answer that best applies.

- Study involves testing of FDA regulated drugs or biologics (See HELP)
- Study is funded by the NIH, and meets the definition of a "clinical trial" (see HELP)
- Study meets the ICMJE definition of a "clinical trial" (See HELP)
- Additional funding agency or journal requires clinical trial registration
- None of the above

If you selected 1, 2, 3, or 4 you must register your trial with ClinicalTrials.gov through the Rockefeller University institutional account. Please contact the Clinical Research Support Office [name] for assistance.

## 9.0

### Study Overview/Summary

#### 9.1 \* Who initiated this study?

Please specify one:

- Principal Investigator Initiated
- Industry Initiated
- Other

**9.2 \*Are other institutions involved in the study?**

- No
- Yes

**9.3 \* Is this a multi-site trial using a single IRB (sIRB) review arrangement? Please see help bubble for definition.**

- Yes
- No

**9.4 \* Who (What) is to be studied?**

- Human Subjects - including coded samples and/or data with links to Identifiers
- Deidentified Samples - unable to be linked to identifiers by receiver
- Data Only - unable to be linked to identifiers
- Identifiable samples or data for exemptions (per 104 (s)(4))

**9.5 \*Study Type:**

- Interventional
- Observational

**9.6 The initial date of IRB approval/determination was:**

02/07/2013

**9.7 \* What is the expected duration of the study?**

10 years

**9.8 \* Are any of the following agents to be used in the study?**

Check all that apply:

- FDA Approved Drug
- FDA Approved Drug for Off-Label Purpose (This might require an IND)
- Investigational New Drug
- Biologic Agents
- Nutritional Supplements
- Placebo
- Vaccines
- No Agents
- FDA Exemption to use Study Drug

#### **9.9 \* Are investigational devices to be used in the study?**

Yes  No

#### **9.15 Special Research Procedures**

Does the study propose to directly involve participants in the following special research procedures?

- Recombinant DNA
- Gene Therapy
- Fetal Tissue
- Embryonic Stem Cells
- Induced Pluripotent Stem Cells
- CRISPR-Cas9

If any item is checked, please see Help for details.

#### **9.16 \* Radioactive Isotopes Involved**

Will participants be exposed to any radiation other than routine x-rays solely for clinical care purposes?

Yes  No

### **10.0 Interventional**

#### **10.1 \*Interventional, please specify:**

- Open Label
- Single Blind
- Double Blind
- Other

### **11.0 Study Phase:**

#### **11.1 Study Phase:**

Select where applicable

- Phase 0
- Phase I
- Phase I/II
- Phase II
- Phase III
- Phase IA
- Phase IB
- Phase IIA
- Phase IIB
- Phase IB/IIA
- Phase IIB/IIIA
- Phase IIIA
- Phase IIIB
- N/A

## 12.0 Objectives and Rationale

### 12.1 \* Overview

Briefly state the **purpose of this study**. Give enough background and rationale to provide both scientists and lay members of the IRB and ACCTS with the basis for exposing human participants to the risks involved.

Antibodies represent an important link between the adaptive and innate immune systems. IgG antibodies are bifunctional molecules comprised of a Fab domain, which determines binding specificity through the variable region, and an Fc domain, which interacts with a variety of receptors on immune cells to confer effector function to IgG molecules. These effector functions include positive regulatory mechanisms such as the activation of antibody-dependent cellular cytotoxicity (ADCC), phagocytosis, and pro-inflammatory cytokine production, as well as negative regulatory functions, such as inhibition of inflammatory immune responses. Effector functions are conferred via the Fc domain through specific amino acid residues in the Fc and the precise glycan composition of an N-linked, complex, biantennary glycan that regulates interactions with members of the IgG Fc receptor (FcR) family and the DC-SIGN family of molecules (1, 2).

The Fc glycan is a powerful regulator of antibody effector function and its specific composition can determine whether an antibody has pro- or anti-inflammatory activity *in vivo* (3-6). For example, the presence of terminal sialic acid on the Fc glycan converts IgGs to anti-inflammatory molecules in a variable region-independent manner. This is exemplified in studies demonstrating that the therapeutic, anti-inflammatory activity of intravenous immunoglobulin (IVIG) is conferred solely through the fraction of IVIG containing Fc glycans terminating in sialic acid, which have been shown to interact with SIGN molecules expressed by innate immune cells (4, 7). Similarly, the presence or absence of a branching fucose moiety modulates the interaction of the IgG Fc with activating Fc receptors to enhance or inhibit IgG mediated cellular cytotoxicity (6, 8, 9).

Though the precise saccharide composition of Fc glycans is known to be a significant determinant of the biologic activity of IgGs, little is known about how the composition is regulated or about the biological consequences of specific modifications. Interestingly, it has been observed in mice and in humans that exposure to immunogens can result in various modifications of the IgG glycan (4, 10).

We plan to study this phenomenon using seven different FDA-approved vaccines; by characterizing Fc glycans in pre- and post- immunization sera, we will define the type of antigen(s) that can elicit changes in Fc glycan composition in humans. We will also study whether healthy adults who have been previously infected with a flavivirus or alphavirus (dengue, zika or chikungunya) generate distinct Fc glycoforms after vaccination compared with healthy adults who have not had known infection with dengue, zika or chikungunya virus infection; for this study we will use the **seasonal inactivated influenza** vaccine because influenza reagents for analysis of the TIV-elicited IgGs are abundant and readily available.

We will also use existing serum samples from controlled influenza virus infection studies performed at the NIAID in order to study how specific Fc glycoforms on influenza-specific IgGs may change during infection and to compare Fc glycan modulations that may occur during infection with those elicited by vaccination. In addition, we will use existing serum samples from a study performed at Emory University. These samples were drawn from patients with dengue virus infection, during acute infection, following defervescence and 1-2 months post infection. We will use these samples to study how Fc glycoforms on dengue envelope protein-specific IgGs may change during infection and we will compare any changes with those observed on IgGs from patients with influenza virus infection.

That antigen exposure can modify Fc glycan composition suggests a possible role for cognate B cell - T cell interactions in the regulation of glycan composition. Accordingly, a second phase of this study will investigate whether T cell help is required for vaccine-elicited glycan modification. We will study this by comparing serum IgG Fc glycan profiles in volunteers who were vaccinated with either T cell dependent (TD) or T cell independent (TI) vaccine antigens. We will also evaluate whether the age of the patient or route of vaccine administration are determinants of vaccine-elicited glycan modification. Finally, we plan to study how specific IgG glycan modifications regulate immunity against *Streptococcus pneumoniae* and against influenza viruses in *in vitro* and *in vivo* models of infection.

**12.4 \* Engaging Stakeholders: Describe any plans to engage other stakeholders (Scientists, practitioners, patients, advocacy groups, etc.) for hypothesis generation, or feasibility purposes.**

The Principal Investigator as well as other members of the [name] laboratory were involved in the hypothesis generation and the feasibility purposes of this application.

**12.5 \* Hypothesis**

Describe the **research hypothesis** in a single sentence.

The saccharide composition of human IgG Fc glycans determines effector function of pathogen-specific IgGs during infection and may be distinct in people with prior symptomatic flavivirus or alphavirus infection, can be modulated by exposure to specific types of vaccine antigens or modulated during viral infection.

**12.6 \* Aim(s)**

Indicate how you will **address the hypothesis** (e.g., to compare groups, to estimate a parameter, to ascertain feasibility). Since the sample size determination is usually based on the primary aim only, the primary aim should be sufficient to justify the study.

**Aim 1:**

To determine whether vaccination can elicit modifications in Fc glycan composition and, if so, whether the T cell dependence of a vaccine antigen, age of the patient at vaccination or route of vaccine exposure regulate observed modifications in the IgG Fc glycan.

**Aim 2:**

To determine how specific components of the IgG Fc glycan regulate immunity against influenza viruses and against *Streptococcus pneumoniae* in *in vitro* and *in vivo* models of infection.

**Aim 3:**

To determine whether infection with influenza virus or dengue virus infection can elicit modifications in Fc glycan composition and to compare any changes with those observed following vaccination.

**Aim 4:**

To determine whether people who develop clinically significant flavivirus or alphavirus (dengue, zika or chikungunya) infection produce distinct Fc glycans in response to vaccination.

**Aim 5:**

To determine the Fc glycosylation status and *in vivo* activity of IgG4 antibodies from patients with IgG4 diseases

**12.7 \* Primary Outcome(s)**

Indicate which **variable(s)** will be assessed to judge the primary specific aim. Give measurement units, if applicable.

**Determination of saccharide components of the IgG Fc glycan pre- (day 0) and post- (day 7 and day 21) vaccination with different vaccines and before, during and following influenza virus infection:**

- The degree of galactosylation, fucosylation and sialylation of pre- vs. post- vaccination Fcs determined by lectin blot (*Erythrina cristagalli*, *Aleuria Aurantia Lectin* and *Sambucus nigra* lectins specific for galactose, fucose and 2,6-sialic acid, respectively).
- Characterization of glycan composition by mass spec analysis.

**Determination of the role of route of antigen exposure, age of the patient, or past flavivirus or alphavirus infection in regulation of Fc glycan modifications.**

- Using three influenza virus vaccines (two inactivated that are administered either intramuscularly or intradermally, and one live that is administered intranasally) we will compare how the route of administration affects modifications of the Fc glycan by western blot and mass spec analysis.
- By comparing vaccine responses in patients < 65 or ≥65 of years of age we will determine how age regulates post-vaccination modifications of the Fc glycan.

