**215 volunteers who meet all the eligibility criteria will be enrolled in this study.**

The study is divided into 3 arms. The groups are defined as follows:

**Arm I: Age 18-64 group:** Groups of 10 study participants each (except for group 2 which includes 25 participants) < 65 years of age (< 50 years of age for Flumist vaccine and < 55 years of age for meningococcal vaccines) will be **vaccinated with one of seven FDA approved vaccines (85 participants total):** **Group 1)** Fluzone intradermal influenza virus vaccine, **Group 2)** Fluzone intramuscular influenza virus vaccine, **Group 3)** Pneumovax 23 (plain polysaccharide pneumococcal vaccine), **Group 4)** Prevnar/PCV13 (pneumococcal conjugate vaccine), **Group 5)** MPSV4 (plain polysaccharide meningococcal vaccine), **Group 6)** Mencevo (meningococcal conjugate vaccine), **Group 10)** Flumist Quadrivalent (intranasal influenza live vaccine).

**Arm II: Age 65-80 group:** Groups of 10 study participants ≥65 years of age will be **vaccinated with one of three of the FDA approved vaccines (30 participants total):** **Group 7)** Fluzone intramuscular influenza virus vaccine, **Group 8)** Pneumovax 23, **Group 9)** Prevnar. Meningococcal vaccines, the intradermal influenza vaccine and intranasal Flumist will not be administered to participants in Arm II.

**Arm III: Healthy adults, age 18-80, with a specific medical history as described here and in Section 12.11 (Inclusion Criteria):** Groups of 25 study participants will be vaccinated with the Fluzone intramuscular influenza virus vaccine (100 participants total). **Group 11)** Prior diagnosis of dengue fever or dengue virus infection. **Group 12)** Prior diagnosis of dengue hemorrhagic fever. **Group 13)** Prior diagnosis of chikungunya virus infection. **Group 14)** Prior diagnosis of zika virus infection

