**The study will occur in four phases:**

**Phase 1:** Volunteers will be recruited to receive influenza vaccines (Groups 1, 2, 7, 10). Recruitment for Groups 1 and 7 will occur simultaneously and volunteers will be enrolled sequentially - enrollment into Group 1 will be given priority over Group 2 because the intradermal vaccine preparation for the 2012-13 influenza season will expire earlier than the intramuscular preparation (April 2013 vs. June 2013). Volunteers will be recruited to receive the Flumist influenza vaccine (Group 10) beginning fall of 2013.

**Phase 2:** Volunteers will be recruited to receive one of the pneumococcal vaccines (Groups 3, 4, 8, 9)

- these subjects will be recruited simultaneously and will be randomized to receive either the Pneumovax or Prevnar vaccines.

**Phase 3:** Volunteers will be recruited to receive one of the meningococcal vaccines (Groups 5 and 6) - these subjects will be recruited simultaneously and will be randomized to receive either the MPSV4 or Menveo vaccines.

**Phase 4:** Volunteers will be recruited for Arm III of the study to receive the Fluzone intramuscular vaccine (Groups 11-14)

Study participants will not be blinded. During the analysis phase, samples will be coded so that the precise vaccine administered within each phase is unknown.

Study visits will be scheduled as follows for groups 1-10: screening, day 0 (within 4 weeks of screen), day 7 safety visit, and weeks 3, 5, 7, 9, and 12. On Day 3-4, a telephone call will be made to check on subject's medical status.

Groups 11-14 will be scheduled as follows: day 0 (within 4 weeks of screen), day 7 safety visit, and week 3. We will not collect samples at weeks 5, 7, 9 or 12 for Groups 11-14 because our existing data on intramuscular Fluzone immunization from Group 2 demonstrate that the major Fc glycan modifications occur during the first 3 weeks following vaccination.

**We do not anticipate any safety issues related to this protocol as all vaccines to be used have been FDA approved and all study participants are healthy adults.**

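### The intranasal arm of the primary route comparison (Group 10 vs Groups 1 and 2) cannot be read as a route effect; only intradermal vs intramuscular Fluzone can address route, and that contrast is not randomised

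*Combined protocol and SAP*

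**What the plan says.** Section 12.7 (Primary Outcomes) includes the role of route of antigen exposure. The three influenza vaccines are described as "two inactivated that are administered either intramuscularly or intradermally, and one live that is administered intranasally", and with them "we will compare how the route of administration affects modifications of the Fc glycan by western blot and mass spec analysis". Aim 1 in 12.6 likewise asks whether route regulates the modifications seen.

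The groups come from the Study Design in 12.9. Group 1 is Fluzone intradermal (n = 10), Group 2 is Fluzone intramuscular (n = 25) and Group 10 is FluMist intranasal (n = 10). Arm I is under 65 in general, with lower limits for some products: "< 50 years of age for Flumist vaccine and < 55 years of age for meningococcal vaccines".

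On allocation, Phase 1 states "Recruitment for Groups 1 and 7 will occur simultaneously and volunteers will be enrolled sequentially", and "enrollment into Group 1 will be given priority over Group 2 because the intradermal vaccine preparation for the 2012-13 influenza season will expire earlier" (April 2013 against June 2013). For the intranasal group, "Volunteers will be recruited to receive the Flumist influenza vaccine (Group 10) beginning fall of 2013". No randomisation is stated for Phase 1. Phase 2, by contrast, says "these subjects will be recruited simultaneously and will be randomized to receive either the Pneumovax or Prevnar vaccines", and Phase 3 has the same provision for the meningococcal vaccines.

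For comparisons across groups, 12.10 plans Repeated Measures ANOVA, descriptive graphics and possibly fitted curves. It names no covariate. The sample size for Groups 1-10 in 12.11 rests on a within-group pre-post paired t-test.

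**The concern.** A statement that route affects the Fc glycan needs groups that differ in route and in little else that could move the endpoint. Group 10 differs from the Fluzone groups in product type, age range and starting season. The protocol itself treats age as a possible determinant of the same glycan changes, since Aim 1 and 12.7 both name it. By its own reasoning, then, the age difference is a potential confounder.

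If the plan is followed as written, a live-vaccine, age or season difference could be published as a primary finding about route. The intradermal versus intramuscular contrast is cleaner, but calling it simply a comparison of routes would hide that participants were not allocated at random.

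**Working it through.** **1. What differs in each contrast**

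| Feature | ID (Group 1) vs IM (Group 2) | Intranasal (Group 10) vs Groups 1 and 2 |
|---|---|---|
| Route | differs | differs |
| Live or inactivated | both inactivated | live vs inactivated |
| Age limit | both under 65 | under 50 vs under 65 |
| Start | both from the 2012-13 preparations, Group 1 with priority | fall 2013 vs 2012-13 preparations |
| Randomised | not stated | not stated |

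Every intranasal participant receives the live vaccine and no injected participant does. An indicator for route and an indicator for vaccine type would be the same column in any model, so no covariate adjustment can separate them. Age can be handled by restriction or adjustment. Season can be handled only if some Fluzone participants were enrolled in the same season as Group 10.

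**2. The plan's own sample size**

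Inputs from 12.11: difference 10 points, SD 4.4 × 1.30 = 5.72, alpha 0.05 / 3 = 0.017, power 80%, two-sided paired t-test.

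- n = 6: noncentrality 10 / (5.72 / √6) = 4.28, power 0.742.
- n = 7: noncentrality 10 / (5.72 / √7) = 4.63, power 0.862.

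The stated n = 7 reproduces. Allowing for 20% non-response and 10% drop-out, 7 / (0.8 × 0.9) = 9.7, hence 10. This sizes the change within a group, not a difference between routes.

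**3. Illustration of a non-route shift**

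Assumptions, none given in the documents for this contrast: the true route effect is zero, the SD of change is 5.72 in each group, the test is an unpaired two-sided t-test on change (a simplification of the planned ANOVA), and season, age or product type shifts the change by 2.5, 5 or 7.5 points. Evaluable numbers use the plan's own losses: 10 × 0.8 × 0.9 = 7.2, taken as 7, and 25 × 0.8 × 0.9 = 18.

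Standard error = 5.72 × √(1/n1 + 1/n2):

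- 7 vs 7 (Group 10 vs Group 1): 3.06
- 7 vs 18 (Group 10 vs Group 2): 2.55

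Noncentrality = shift / standard error; for example, 5 / 3.06 = 1.64 for 7 vs 7. The noncentral t distribution then gives the chance of declaring a route difference:

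| Assumed shift | 7 vs 7, alpha 0.05 | 7 vs 18, alpha 0.05 | 7 vs 7, alpha 0.017 | 7 vs 18, alpha 0.017 |
|---|---|---|---|---|
| 2.5 | 12% | 16% | 5% | 7% |
| 5 | 33% | 47% | 17% | 29% |
| 7.5 | 62% | 81% | 41% | 65% |

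The nominal rates are 5% and 1.7%.

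**The case against.** - **The limitation is partly disclosed and the comparison is subsidiary.** 12.7 says in the same sentence that one vaccine is live, Aim 1 makes route conditional on finding a vaccination effect, and the sample size rests on the pre-post test. This stands as mitigation. But route is still listed under primary outcomes, and no text limits what may be concluded from the intranasal group.
- **Baselines and coding reduce bias.** Each participant has a day 0 sample, and samples are coded for analysis. These deal with differences in starting level and with assay bias. They do not make the groups alike in how they respond.
- **There was a practical reason for the order.** Initial IRB approval was 02/07/2013 and the intradermal preparation expired in April 2013, leaving under three months. That explains "enrollment into Group 1 will be given priority over Group 2" and is a fair defence of the conduct, but it does not make the contrast randomised.
- **Stronger readings go too far.** A reader might infer that no part of the route outcome can address route. The documents do not support that: Groups 1 and 2 share inactivated type and the under-65 limit. A reader might also infer that Group 2 opened only once Group 1 was full, or that Group 10 and Group 2 fell wholly in different seasons. The text gives priority, not strict succession, and does not say when Group 2 closed.
- **Randomising Groups 1 and 2 is no longer open.** The Study Design already cites existing Group 2 data, and the Protocol Timeline cites data from 2012-13 Fluzone recipients. Adjusting for date is not a safe substitute: if Group 1 was enrolled largely before Group 2, date and group are nearly collinear.

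**Conclusion.** The point holds for the intranasal contrast. Route is fully aliased with live versus inactivated type, and the lower age limit and later start add to the problem. The planned analysis resolves none of these, so 12.7 should not attribute a Group 10 difference to route. Intradermal versus intramuscular Fluzone remains the one contrast that can address route, as a non-randomised comparison.

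The documents give no size for the bias. The figures of 12% to 62% (7 vs 7) and 16% to 81% (7 vs 18) at 0.05, or 5% to 41% and 7% to 65% at 0.017, depend on the assumed shifts, the SD of 5.72, the evaluable numbers and the simplified test. They show that shifts smaller than the planned 10-point effect could matter, not that such shifts exist. No single figure from that table should be quoted as the error rate of the study.

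**What to change.** In 12.7, with a matching sentence in 12.10:

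1. Limit the route inference to intradermal versus intramuscular inactivated Fluzone of the same season. State that the comparison is non-randomised and that Group 1 had enrolment priority, and adjust for age.
2. Report vaccination dates by group. Adjust for date only as a sensitivity analysis, and only if the dates overlap.
3. Report FluMist versus Fluzone as a comparison of a live intranasal product with inactivated injected products, restricted to participants under 50 and adjusted for age. State season as an unresolved difference unless Group 2 includes participants vaccinated in the same season as Group 10.

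The cost is a narrower claim for the intranasal vaccine and fewer Fluzone comparators once those aged 50 and over are left out. The documents do not say how many that would be. Age and vaccination date should already be on record, so no new participants or assays are needed.
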